### **7.1.5. Temperature**

Temperature will be measured orally. No eating, drinking or smoking is allowed for 15 minutes prior to the measurement.

### **7.1.6. Electrocardiogram**

ECGs should be collected at times specified in the [Schedule of Activities](#).

All scheduled ECGs should be performed after the subject has rested quietly for at least 10 minutes in a supine position.

Triplicate 12-lead ECGs (**Day 1 only**) will be obtained approximately 2-4 minutes apart; the average of the triplicate ECG measurements collected at each nominal time point on Day 1 will serve as each subject's baseline QTcF value.

To ensure safety of the subjects, a qualified individual at the investigator site will make comparisons to baseline measurements. If the QTcF interval is increased by  $\geq 45$  msec from the baseline, or an absolute QTcF value is  $\geq 500$  msec for any scheduled ECG, then 2 additional ECGs will be collected, approximately 2-4 minutes apart, to confirm the original measurement. If either of the QTcF values from these repeated ECGs remains above the threshold value ( $\geq 45$  msec from the baseline; or is  $\geq 500$  msec), then a single ECG must be repeated at least hourly until QTcF values from 2 successive ECGs fall below the threshold value that triggered the repeat measurement.

If the average of QTcF values from the triplicate measurements remains above the threshold value ( $\geq 45$  msec from the baseline; or is  $\geq 500$  msec), then a single ECG must be repeated at least hourly until QTcF values from 2 successive ECGs fall below the threshold value that triggered the repeat measurement.

If QTcF values remain  $\geq 500$  msec (or  $\geq 45$  msec from the baseline) for greater than 4 hours (or sooner at the discretion of the investigator); or QTcF intervals get progressively longer, the subject should undergo continuous ECG monitoring. A cardiologist should be consulted if QTcF intervals do not return to less than 500 msec (or to  $< 45$  msec above the baseline) after 8 hours of monitoring (or sooner at the discretion of the investigator).

In some cases, it may be appropriate to repeat abnormal ECGs to rule out improper lead placement as contributing to the ECG abnormality. It is important that leads are placed in the same positions each time in order to achieve precise ECG recordings. If a machine-read QTcF value is prolonged, as defined above, repeat measurements may not be necessary if a qualified physician's interpretation determines that the QTcF values are in the acceptable range.

### **7.1.7. Injection and Infusion Site Reactions**

Injection site reactions will be assessed according to the [Schedule of Activities](#). Injection site reactions may include but are not limited to: erythema, induration, ecchymosis, pain and pruritus. The size and severity of injection site reactions will be assessed and documented. If deemed appropriate by the investigator, a consultation with a dermatologist will be performed. Documentation may include a dermatologist report, clinic notes and photographs.

## 7.2. Efficacy

### 7.2.1. Hemophilic Bleeding Episodes

During this study, the investigator (or qualified designee) will review the subject diary with the subject, and inquire about and record AEs, concomitant treatments, bleeding episodes (including location and etiology – traumatic or spontaneous) and any hemostatic treatments (including intravenous treatments with factor VII products, factor IX products or bypass agents). Hemostatic therapy that is administered to treat bleeding episodes during the Screening period and during the study through the final study visit will be documented as concomitant treatment. Subject diary review will include any bleeding episodes treated with hemostatic agents. Bleeding episodes requiring treatment with intravenous coagulation factor products or bypass agents will count toward the determination of bleeding episode frequency during the period of treatment with PF-06741086. Subject assessment(s) will be captured on the subject diary and reviewed by the investigator at study visits. One assessment per infusion will be required.

### 7.2.2. Bleeding

Occurrences of bleeding episodes treated with hemostatic agent(s) will be obtained from subject diaries and medical records. Where relevant, investigators (or designee) and monitors will ensure that there is consistency between the subject's medical record and/or subject diaries and the CRFs. Bleeding episodes will not be reported as AEs unless associated with a serious adverse event, although the concomitant events associated with a bleed may be reported as an AE if appropriate (eg, a fracture, pain – see [Section 8.6](#) below for guidance on hemophilia related events). Both spontaneous bleeding episodes and traumatic bleeding episodes will be collected. Only bleeding episodes that are considered serious and meet the SAE criteria should be listed on the AE CRF page. When bleeding episodes that meet the SAE criteria are recorded on the AE CRF, the location (site) of the bleed and the etiologic classification as spontaneous or traumatic should be included (as described in [Section 7.2.1](#) and [Section 7.2.3](#)). The subject diary or medical record will serve as the source document for bleeding episodes during the study. Investigators (or designee) and/or monitors will review the subject's diary/medical records to assist in classification if necessary.

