#### **7.2.4. Location of Bleeds**

For the purposes of this study, when subjects report a bleed treated with hemostatic therapy, the location of the bleed should be recorded in the subject diary or medical record. Bleeds will be reported as occurring in 1 of the following locations: joint, muscle/soft tissue, or other. Each individual location of multiple-site bleeds will be reported. For joint bleeds, the specific joint will be reported. Parameters to identify joint bleeds include: pain on joint motion, limitation of motion, and visible swelling of joint.

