## **8. ADVERSE EVENT REPORTING**

### **8.1. Adverse Events**

All observed or volunteered AEs regardless of treatment group or suspected causal relationship to the investigational product(s) will be reported as described in the following sections.

For all AEs, the investigator must pursue and obtain information adequate both to determine the outcome of the AE and to assess whether it meets the criteria for classification as a serious adverse event (SAE) requiring immediate notification to Pfizer or its designated representative. For all AEs, sufficient information should be obtained by the investigator to determine the causality of the AE. The investigator is required to assess causality. Follow-up by the investigator may be required until the event or its sequelae resolve or stabilize at a level acceptable to the investigator, and Pfizer concurs with that assessment.

As part of ongoing safety reviews conducted by the Sponsor, any nonserious AE that is determined by the Sponsor to be serious will be reported by the Sponsor as an SAE. To assist in the determination of case seriousness, further information may be requested from the investigator to provide clarity and understanding of the event in the context of the clinical study.

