### **8.6. Hemophilia Events**

Hemophilia events are certain AEs that are likely to occur due to the subject's hemophilia. For example, pain, swelling, or decreased range of motion due to a bleed may be an expected consequence of hemophilia (the bleeding episode itself is not reported as an AE, unless the bleeding episode meets the criteria for a Serious Adverse Event, see [Section 8.7](#)). Investigators should determine if an AE is expected because of the subject's hemophilia. Bleeding or bruising, not due to the subject's hemophilia, will be recorded as an AE, and not a hemophilia event. Hemophilia events that require hospitalization or meet other SAE criteria should be reported as SAEs.

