3.1.1. Adverse Events

Any events occurring following start of treatment or increasing in severity will be counted as treatment emergent.

Events that occur in a non-treatment period (applies to screening only) will not be counted as treatment emergent as this is a single-period study.

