6.5. Safety Summaries and Analyses

6.5.1. Adverse Events

Adverse events (AEs) will be reported in accordance with the sponsor reporting standards. AEs will also be summarized separately by inhibitor status, if applicable.

In addition, thrombotic events will be listed and summarized by dose level and cohort if data permits. A list of thrombotic events is provided in Appendix 1 of the protocol. If the subject has received concomitant administration of a bypass agent (ie, NovoSeven, NovoSeven RT, Niasbase, eptacog alfa, FEIBA, Activated prothrombin complex concentrate, APCC, anti-inhibitor coagulant complex concentrate) at the onset of a thrombotic event, the type and dose of bypass agent will be presented as well.

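### Recording non-serious symptoms of a bleed as AEs is optional in one protocol section and required by others, and the SAP never separates them, so the all-cause TEAE frequency by dose can follow site convention and bleeding.

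*Protocol*

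**What the plan says.** **Protocol, how bleeds and their symptoms are recorded**

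- Section 7.2.2: a bleed is not an AE unless serious, but "the concomitant events associated with a bleed may be reported as an AE if appropriate". The examples are a fracture and pain, and the reader is sent to Section 8.6 for guidance.
- Section 8.6: "Hemophilia events are certain AEs that are likely to occur due to the" subject's hemophilia. Its examples are pain, swelling and reduced range of motion from a bleed. Investigators must decide whether an AE is expected because of hemophilia. Events meeting SAE criteria are reported as SAEs. Nothing is said about where a non-serious hemophilia event is recorded.
- Section 8.1: "All observed or volunteered AEs regardless of treatment group or suspected causal relationship" are to be reported. Section 8.15.3 puts all AEs on the AE page of the CRF.
- Section 7.2.4: "Parameters to identify joint bleeds include: pain on joint motion, limitation of motion, and visible swelling of joint". These are essentially the signs that 8.6 gives as examples of hemophilia events.

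**Endpoint and analysis**

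- Protocol 2.2.1 makes the frequency, severity and causal relationship of TEAEs, Day 1 to Day 113, a primary endpoint. Section 9.6 summarizes incidence and severity by dose level.
- SAP 3.1.1: "Any events occurring following start of treatment or increasing in severity will be counted as treatment emergent".
- SAP 6.5.1: "Adverse events (AEs) will be reported in accordance with the sponsor reporting standards", with a further split by inhibitor status and a summary of thrombotic events. SAP 6.1 adds tables by dose level and cohort and, if data permit, by hemophilia type. Hemophilia events are not mentioned.

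**The concern.** Non-serious bleeds are kept out of the AE data because they are counted as efficacy. Their symptoms can come back in as AEs, and whether they do depends on how a site reads 7.2.2. An investigator who follows 8.1 and 8.15.3 records knee pain from a joint bleed as a TEAE; one who takes 7.2.2 at its word may not. Both have followed the protocol.

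Two things are at stake in reading the primary safety tables. First, with 6 subjects per cohort, a difference in convention between a few sites can move a cohort's TEAE incidence visibly. Second, where symptoms are recorded, TEAE incidence partly follows the bleed rate. A dose that prevents fewer bleeds would then show more TEAEs for a reason unrelated to toxicity, which could blur or counter a real dose trend.

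**Working it through.** The conflict is one of wording, and no figure in the plan depends on it. The arithmetic only shows its scale.

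**Text.** Three readings have to be reconciled for a non-serious symptom of a bleed:

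1. 7.2.2 permits an AE record.
2. 8.1 with 8.15.3, and the first sentence of 8.6, require one.
3. 8.6, the section to which 7.2.2 refers for guidance, asks for a classification but attaches no recording consequence to it.

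The SAP then counts whatever was recorded, with no mark by which to separate it.

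**Inputs.** Protocol 9.1: control rate 2.36 bleeds per patient-month, 3 months, 85% reduction, 6 subjects per cohort. Assumed, because the documents do not give them: a comparison cohort with a 50% reduction; negative binomial dispersion k = 1 as an alternative to Poisson; the share q of bleeds that yield a recorded symptom; a background incidence b of other TEAEs, independent of bleeding.

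**Mean bleeds per subject.** m = 2.36 × 3 × (1 − reduction).

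- 85% reduction: 7.08 × 0.15 = 1.062
- 50% reduction: 7.08 × 0.50 = 3.54

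**Share of subjects with at least one recorded bleed symptom.** Poisson: 1 − exp(−qm). Negative binomial with k = 1: qm / (1 + qm).

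| q | Model | 85% reduction | 50% reduction | Gap (points) |
|---|---|---|---|---|
| 1 | Poisson | 65.4% | 97.1% | 32 |
| 1 | k = 1 | 51.5% | 78.0% | 26 |
| 0.5 | Poisson | 41.2% | 83.0% | 42 |
| 0.25 | Poisson | 23.3% | 58.7% | 35 |
| 0 | either | 0% | 0% | 0 |

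At the planned effect and q = 1 this is 6 × 0.654 = 3.9 or 6 × 0.515 = 3.1 subjects in a cohort of 6.

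The share affected is largest at q = 1, so 52% to 65% is a ceiling on it for the 3-month period. The gap between cohorts is not largest at q = 1. Under Poisson it is wider at a quarter or a half, because full recording brings the 50%-reduction cohort close to 100%. The 26 to 32 points should be read as the full-recording case, not as a maximum over q.

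**Allowing for other TEAEs.** A subject who has another TEAE is already counted, so each share and gap is multiplied by (1 − b). Poisson, q = 1, b = 0.5 to 0.7:

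- Gap: 31.7 × 0.5 = 15.8 and 31.7 × 0.3 = 9.5, so about 16 down to 10 points.
- Extra subjects per cohort at the planned effect: 3.93 × 0.5 = 2.0 down to 3.93 × 0.3 = 1.2.
- At q = 0.5 the gap is 41.8 × 0.5 = 20.9 down to 41.8 × 0.3 = 12.5 points.

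**Window.** The TEAE window runs to Day 113. If the same rate held for 112 days (3.68 months), the q = 1 shares at 85% reduction would be 73% (Poisson) and 57% (k = 1).

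**The case against.** The best case on the other side is that this is loose wording with limited consequences. The word "may" in 7.2.2 can be read as qualifying the bar on reporting bleeds: the bleed stays off the AE page, but accompanying events are not barred. On that reading it is compatible with 8.1. Safety is descriptive, and SAP 6.1 plans no formal analysis. Protocol 3.3 does not limit escalation by comparing TEAE incidence between doses, and its individual dose-modification rule already exempts complications of hemophilia. Causality is recorded for every AE. The sponsor reporting standards and the CRF are not among the documents and might already separate these events.

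Most of this stands as a limit on the harm. Symptoms judged unrelated would fall out of a related-TEAE table, so that table is less affected. It does not protect the all-cause frequency, which is also part of the endpoint. The compatible reading of 7.2.2 is possible, but a site is not obliged to adopt it. Separation under unseen standards cannot be excluded, but the SAP does not state it.

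Three stronger readings may occur to a reader, and the documents do not support them:

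- *That 8.6 makes hemophilia events a category apart from AEs.* The words "will be recorded as an AE, and not a hemophilia event" concern bleeding or bruising that is not due to hemophilia; they say that such an AE does not take the hemophilia label. The section opens by treating hemophilia events as AEs.
- *That 7.2.2 bars non-hemophilic bleeding from the AE page.* "Only bleeding episodes that are considered serious and meet the SAE criteria should be listed on the AE CRF page" stands in the efficacy section, in a passage about bleeds treated with hemostatic agents. Section 8.6 covers bleeding not due to hemophilia. The two are best read as covering different events.
- *That the SAP gives only one set of tables by dose.* It also splits by hemophilia type and inhibitor status and lists thrombotic events. None of these splits isolates hemophilia events.

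**Conclusion.** The point holds in limited form. Followed as written, the protocol leaves the AE recording of non-serious bleed symptoms to investigator discretion in one section and requires it in others, and the SAP has no way to separate the result. The descriptive all-cause TEAE frequency by dose can therefore vary with convention and with bleeding.

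At the planned 85% reduction, convention alone could decide TEAE status for at most 52% to 65% of subjects over 3 months. That ceiling assumes that every bleed yields a recorded symptom and that no subject has another TEAE. At a quarter or half of bleeds it is 23% or 41% (Poisson). Against an assumed 50%-reduction cohort, full recording gives a gap of 26 to 32 points with no difference in toxicity. An assumed background incidence of 50% to 70% reduces the Poisson figure to about 16 to 10 points. The bleed rate and effect size are the protocol's; the dispersion, recording share, background incidence and comparison cohort are assumptions.

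It would go too far to infer that the escalation decision or the related-TEAE results are compromised. The change is worth making because it is cheap and the tables concerned are primary.

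**What to change.** - **Protocol 7.2.2 and 8.6:** replace the optional wording with one rule, stated the same way in both places. Non-serious symptoms of a bleed that are reported as AEs are recorded on the AE CRF page and marked as hemophilia events, using the determination that 8.6 already asks of the investigator. State in 8.6 that a hemophilia event is an AE carrying that mark.
- **SAP 6.5.1:** tabulate TEAE incidence and severity by dose level and cohort twice, for all TEAEs and excluding marked hemophilia events. Read dose trends from both, because fuller recording raises the bleed-driven part of the first table, and the second depends on the investigator's classification.

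The cost is one mark on the CRF, a few sentences of protocol text, one repeated set of tables and slightly more recording by sites. No data are lost, and the all-TEAE result remains available.

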### 7.2.3. Types of Bleeding

For the purposes of this study, a bleed treated with a hemostatic agent will be classified as either spontaneous or traumatic. The criteria for spontaneous and traumatic bleeds are described below.

**Spontaneous Bleeding Episodes:** Bleeding episodes should be classified as spontaneous if a subject records a bleeding event when there is *no known* contributing factor such as definite trauma, antecedent “strenuous” activity, or “overuse”. The determination of “strenuous” or “overuse” is at the discretion of the subject/caregiver/investigator. For example, if a subject were to wake up in the morning and note he was bleeding, a “spontaneous” bleed would be recorded. Target joints can have spontaneous bleeding episodes.

**Traumatic Bleeding Episodes:** Bleeding episodes should be classified as traumatic if a subject records a bleeding event when there is a known or presumed contributing factor/reason for the bleed. For example, if a subject were to exercise “strenuously” and then have a bleed in the absence of any obvious injury, the bleed would be recorded as a traumatic bleed. Target joint bleeding episodes can be traumatic if a known action led to bleeding into the joint.

#### **7.2.4. Location of Bleeds**

For the purposes of this study, when subjects report a bleed treated with hemostatic therapy, the location of the bleed should be recorded in the subject diary or medical record. Bleeds will be reported as occurring in 1 of the following locations: joint, muscle/soft tissue, or other. Each individual location of multiple-site bleeds will be reported. For joint bleeds, the specific joint will be reported. Parameters to identify joint bleeds include: pain on joint motion, limitation of motion, and visible swelling of joint.

#### **7.2.5. Treatment of Bleeding Episodes**

Bleeding episodes that occur during this study may be treated (on-demand) with hemostatic therapy (eg intravenous factor products or rFVIIa bypass agent therapy at approximately 90 µg/kg) as deemed appropriate by the investigator. The specific treatment with hemostatic therapy is at the discretion of the subject/caregiver/investigator, but all doses of hemostatic therapy taken after signing of informed consent will be documented as concomitant medications or concomitant treatments.

If a subject experiences a bleeding episode during the washout period preceding screening laboratory assessments, the subject is to be stabilized utilizing the subject’s usual hemostatic treatment regimen. Once the bleeding episode has been successfully treated a new washout period should be completed prior to obtaining the screening laboratory tests.

If a subject experiences a bleeding episode during the washout period preceding the initial administration of PF-06741086 the subject is to be stabilized utilizing the subject’s usual hemostatic treatment regimen and a new washout period should be implemented. Once treatment of the bleeding episode with hemostatic agents has been completed a new washout period should be initiated in anticipation of the initial treatment with PF-06741086.

If a subject experiences a bleeding episode during the PK assessment period following administration of PF-06741086, the subject is to be stabilized utilizing the subject’s usual factor VIII or factor IX treatment regimen or rFVIIa bypass agent therapy at approximately 90 µg/kg, and protocol specified observations and procedures should proceed to completion. Pausing or withdrawal of treatment with investigational product is not required in the event of a breakthrough bleed, but may be considered at the discretion of the investigator.

### 7.3. Pharmacokinetics (PK)

#### 7.3.1. Plasma for Analysis of PF-06741086

During all study periods, blood samples (4.5 mL) to provide approximately 1.5 mL plasma for PK analysis will be collected into appropriately labeled tubes containing sodium citrate at times specified in the [Schedule of Activities](#). During periods with IV dosing, the PK sample should be taken from the opposite arm from the IV dosing.

The actual times may change but the number of PK samples will remain the same. All efforts will be made to obtain the PK samples at the exact nominal time relative to dosing. Samples should be obtained within the time window specified in the [Schedule of Activities](#); at the end of the IV infusion, samples obtained from 0 to 5 minutes after the end of the infusion will not be captured as a protocol deviation (6 or more minutes after the end of the infusion will be a deviation).

- Details regarding the collection, processing, storage and shipping of the blood samples will be provided in the central lab manual.
- Samples will be analyzed using a validated analytical method in compliance with Pfizer standard operating procedures.
- The PK samples must be processed and shipped as indicated to maintain sample integrity. Any deviations from the PK processing steps, including any actions taken, must be documented and reported to the Sponsor. On a case-by-case basis, the Sponsor may make a determination as to whether sample integrity has been compromised. Any sample deemed outside of established stability, or of questionable integrity, will be considered a protocol deviation.

- CCI [REDACTED]

#### 7.3.2. Shipment of Pharmacokinetic Samples

The shipment address and assay lab contact information will be provided to the investigator site prior to initiation of the study.

